3.3 Treatment at Primary Institution

All investigational agent(s) should be dispensed and all imaging studies obtained at Cincinnati Children's Hospital Medical Center.

3.4 Criteria to Start Treatment

- 3.4.1 Subjects must start therapy within fourteen (14) days of registration.
- 3.4.2 Imaging evaluations necessary to establish eligibility for study entry must be done within four weeks prior to registration.
 - All other evaluations necessary to establish eligibility for study entry must be done within 14 days prior to registration.
- 3.4.3 Laboratory values used to assess eligibility must be no older than seven (7) days prior to the start of therapy. Laboratory tests used to determine eligibility need not be repeated if therapy starts within seven (7) days. If a test that is repeated post registration and prior to the start of therapy is outside the limits for eligibility, it must be rechecked within 48 hours prior to the start of therapy. If the recheck is still outside the limits for eligibility, the patient may not receive protocol therapy and will be considered off study.

4 REGISTRATION PROCEDURES

4.1 IRB Approval

Local IRB/REB approval of this study must be obtained prior to consenting and registration of patients.

4.2 Informed Consent for treatment

Consent should be obtained prior to the initiation of any procedures or assessments performed for the purpose of determining protocol eligibility, which would not otherwise be consistent with the institution's standards of clinical practice.

Prior to consent, the protocol's status should be verified via the CCHMC Phase 1/regulatory teams to ensure the study is open to accrual.

4.3 Patient Registration

Patients must be registered prior to any protocol treatment. Patient registration is only available to authorized personnel at CCHMC. Signing off of the eligibility checklist by Investigator or sub-Investigator completes registration.

5 TREATMENT PLAN

Treatment will be administered on an outpatient basis. Reported adverse events and potential risks are described in Section 7. Appropriate dose modifications are described in Section 6.2. No investigational or commercial agents or therapies other than those described below may be administered with the intent to treat the patient's tumor.

5.1 Drug Administration

For stratum 1 and stratum 2 patients with NF2 dosing will be based on BSA. Dosing is based on BSA calculated at the beginning of each course. Selumetinib will be supplied as 10 mg and 25 mg capsules or currently available formulation. Patients will receive selumetinib orally twice daily approximately 12 hours apart. Four consecutive weeks will constitute one course and subsequent courses will immediately follow, with no scheduled break in the administration of the drug.

The recommended dose of selumetinib is 25 mg/m² of body surface area (BSA), taken orally twice daily (approximately every 12 hours).

Dosing is individualised based on BSA (mg/m^2) and rounded to the nearest achievable 5 mg or 10 mg dose (up to a maximum single dose of 50 mg). Different strengths of selumetinib capsules can be combined to attain the desired dose (Table 1). selumetinib is not recommended in patients with a BSA <0.55 m².

Table 1 Dosing scheme of selumetinib 25 mg/m² twice daily

Body Surface Area (BSA)	Dose in mg (twice daily)
$0.55 - 0.69 \text{ m}^2$	10
$0.70 - 0.89 \text{ m}^2$	20
0.90 – 1.09 m ²	25
1.10 – 1.29 m ²	30
1.30 – 1.49 m ²	35
1.50 – 1.69 m ²	40
1.70 – 1.89 m ²	45
≥1.90 m ²	50

Dosing is based on the BSA calculated at the beginning of each course of therapy for all patients. Dosing reduction tables are available in APPENDIX D. Patients will be provided with a Medication Diary for selumetinib, instructed in its use, and asked to bring the diary and pill bottles with them to each appointment.

Selumetinib capsules must be taken whole (do not crush or chew) and should be taken on an empty stomach (no food or drink other than water) either 1 hour before or 2 hours after meals. Selumetinib capsules should be taken with water only.

Participants should be advised to drink plenty of water or take rehydration fluids to avoid dehydration if diarrhea occurs. Patients who vomit a dose of selumetinib should NOT be redosed, and appropriate anti-emetic therapy should be implemented prior to the next scheduled dose.

Participants should avoid excessive exposure to sunlight. Patients should use adequate sunscreen protection if exposure to sunlight is to be anticipated.

During the studies, participants should avoid consuming large amounts of grapefruits, Seville oranges, or any other products that may contain these fruits, e.g., grapefruit juice, as these may affect selumetinib metabolism.

Participants should avoid donating blood while taking selumetinib and for at least 12 weeks after receiving the last dose of selumetinib.

Unless considered clinically indicated, patients should avoid taking other additional non-study medications that may interfere with the study medications. In particular, patients should avoid medications that are strong inhibitors or moderate/strong inducers of CYP3A4 and fluconazole (potent CYP2C19 and moderate CYP3A4 inhibitor), as this may interfere with the metabolism of selumetinib. See Appendix C.

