6.2.1 Criteria for continued treatment after toxicity

The study chair or co-chair must be notified of any dosage modification prior to the implementation of the dose modification.

Dose de-escalations to dose level -1 are permitted. See Appendix D.

All patients who require dose de-escalation from dose level -1 must be taken off treatment.

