APPENDIX D: Dose Reduction Guide for Selumetinib

Body Surface Area (m ²)		Selumetinib dose (mg) Dose level 0			First dose reduction (mg)		
					Dose level -1		
] [a	am	pm		am	pm	
0.55 to 0.69	7	10	10		10	Zero	
0.7 to 0.89		20	20		20	10	
0.9 to 1.09	1 [25	25		25	10	
1.1 to 1.29	1 [30	30		25	20	
1.3 to 1.49	1 [35	35		25	25	
1.5 to 1.69	1 [40	40		30	30	
1.7 to 1.89	7 [45	45		35	30	
1.9 to \geq 2.0		50	50		35	35	

For all patients, dosing will be based on BSA.

Dosing Table for AZD 6244 20 mg/m2 BID

Dose Level	BSA Adjusted Total Daily	BSA	Range	Morning Pills Required		Evening Pills Required	
(mg/m ² BID	Dose (mg)	low	high	10 mg	25 mg	10 mg	25 mg
	20	0.50	0.65	1	0	1	0
	30	0.66	0.81	2	0	1	0
	35	0.82	0.93	0	1	1	0
	40	0.94	1.06	2	0	2	0
	45	1.07	1.18	0	1	2	0
	50	1.19	1.31	0	1	0	1
^	55	1.32	1.43	3	0	0	1
20 mg/m² BID	60	1.44	1.56	3	0	3	0
n^2	65	1.57	1.68	1	1	3	0
1/80	70	1.69	1.81	1	1	1	1
0 п	75	1.82	1.93	4	0	1	1
61	80	1.94	2.06	4	0	-4	0
	85	2.07	2.18	2	1	4	0
	90	2.19	2.31	2	1	2	1
	95	2.32	2.43	0	2	2	1
	100	2.44	2.56	0	2	0	2
	105	2.57	2.68	3	1	0	2
	110	2.69	2.81	3	1	3	1
	115	2.82	2.93	1	2	3	1
	120	2.94	3.00	1	2	1	2

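### At BSA 0.61–0.69 m², Table 1's 10 mg dose departs from section 5.1's own rounding rule, and a second Appendix D table conflicts with it at 0.66–0.69 m²

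*Combined protocol and SAP*

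**What the plan says.** Section 5.1 states the dose and the rule for turning it into capsules:

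- Target: "The recommended dose of selumetinib is 25 mg/m² of body surface area (BSA), taken orally twice daily".
- Rounding: "rounded to the nearest achievable 5 mg or 10 mg dose", "up to a maximum single dose of 50 mg".
- Supply: "Selumetinib will be supplied as 10 mg and 25 mg capsules or currently available formulation".
- Lower limit: "selumetinib is not recommended in patients with a BSA <0.55 m²".

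Table 1 in the same section gives 10 mg twice daily for BSA 0.55–0.69 m² and 20 mg twice daily for 0.70–0.89 m². From there it rises in 5 mg steps to 50 mg at 1.90 m² and above. BSA is recalculated at the start of every course.

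For reductions, section 6.2.1 says: "Dose de-escalations to dose level -1 are permitted. See Appendix D". Appendix D contains two tables:

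- The reduction guide repeats 10 mg morning and evening for 0.55–0.69 m² at level 0. At level -1 it gives 10 mg in the morning and zero in the evening.
- A second table, headed "Dosing Table for AZD 6244 20 mg/m2 BID", gives 20 mg a day for 0.50–0.65 m² and 30 mg a day for 0.66–0.81 m².

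**The concern.** A dose table should follow from the rule printed above it, or say where it departs from that rule. In the upper part of its lowest row, Table 1 does neither: the tabulated dose is further from the 25 mg/m² target than another achievable dose is.

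Appendix D makes this harder to resolve. For the top of the same band, a table headed with a lower mg/m² figure gives a higher daily amount than the nominal full dose. Section 5.1 refers to the Appendix D reduction tables in the plural, so staff could reach either one.

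The stake is dosing instructions for small children that can be read in more than one way. A child growing from 0.69 to 0.70 m² between courses would also go from well below target to somewhat above it in one step. Treatment may run for 26 courses (section 5.5), so this could happen on study.

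**Working it through.** **Inputs.** Section 5.1: 25 mg/m² per dose, nearest achievable dose, 50 mg maximum single dose, 10 mg and 25 mg capsules, and the rows of Table 1. Appendix D: both tables. Assumptions: only 10 mg and 25 mg capsules are used, and BSA is recorded to 0.01 m².

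**Achievable single doses up to 50 mg** (sums of 10s and 25s): 10, 20, 25, 30, 35, 40, 45, 50. Neither 5 nor 15 mg can be made.

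**Step 1: reproduce Table 1.** Target = 25 × BSA. Share of target = table dose ÷ target. The nearest achievable dose was compared with the table at each 0.01 m².

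| BSA (m²) | Table 1 (mg) | Target (mg) | Share of target | Follows the rule? |
|---|---|---|---|---|
| 0.55–0.69 | 10 | 13.75–17.25 | 58.0–72.7% | only at 0.55–0.59; tie at 0.60 |
| 0.70–0.89 | 20 | 17.50–22.25 | 89.9–114.3% | yes |
| 0.90–1.09 | 25 | 22.50–27.25 | 91.7–111.1% | yes |
| 1.10–1.29 | 30 | 27.50–32.25 | 93.0–109.1% | yes |
| 1.30–1.49 | 35 | 32.50–37.25 | 94.0–107.7% | yes |
| 1.50–1.69 | 40 | 37.50–42.25 | 94.7–106.7% | yes |
| 1.70–1.89 | 45 | 42.50–47.25 | 95.2–105.9% | yes |
| 1.90–2.00 | 50 | 47.50–50.00 | 100.0–105.3% | yes |

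The last row is open-ended in the protocol and is taken to 2.00 m² here. Exact ties occur at 0.90, 1.10, 1.30, 1.50, 1.70 and 1.90 m² (for example, 25 × 0.90 = 22.5, midway between 20 and 25). The table rounds up at all six.

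**Step 2: the lowest row in detail.** This is arithmetic on the stated rule, not a dosing view.

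| BSA (m²) | Target (mg) | Distance to 10 mg | Distance to 20 mg | 10 mg as share of target |
|---|---|---|---|---|
| 0.55 | 13.75 | 3.75 | 6.25 | 72.7% |
| 0.59 | 14.75 | 4.75 | 5.25 | 67.8% |
| 0.60 | 15.00 | 5.00 | 5.00 | 66.7% |
| 0.61 | 15.25 | 5.25 | 4.75 | 65.6% |
| 0.69 | 17.25 | 7.25 | 2.75 | 58.0% |

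So 10 mg is the nearest achievable dose at 0.55–0.59 m², ties at 0.60 m², and is not the nearest at 0.61–0.69 m². Under the table's own round-up of ties, 0.60 m² joins the second group. At the row boundary the share goes from 10 ÷ 17.25 = 58.0% (0.69 m²) to 20 ÷ 17.50 = 114.3% (0.70 m²).

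**Step 3: Appendix D, 20 mg/m² table against Table 1 (daily totals).**

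- 0.55–0.65 m²: 20 mg a day in both.
- 0.66–0.69 m²: 30 mg a day in the 20 mg/m² table, against 2 × 10 = 20 mg a day in Table 1 under the 25 mg/m² scheme.

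**Step 4: Appendix D, size of the level -1 step.** Cut = 1 − (level -1 daily total ÷ level 0 daily total).

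- 0.55–0.69 m²: 1 − 10/20 = 50%, leaving one dose a day.
- Other rows, in order: 40→30 (25%), 50→35 (30%), 60→45 (25%), 70→50 (28.6%), 80→60 (25%), 90→65 (27.8%), 100→70 (30%).

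**The case against.** **The rule can be read another way.** Suppose one rounds to the nearest 5 mg first. Every target from 13.75 to 17.25 mg becomes 15 mg, which cannot be made and is equally far from 10 and 20. The row's upper limit fits this reading, because 17.5 mg at 0.70 m² is where rounding up reaches 20. The row would then be a step down from an unachievable dose. This is plausible, but the downward direction is not stated and runs against the table's upward rounding of ties. An unexplained exception still needs an explanation.

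**A deliberate exception is credible.** Applied literally at 0.61–0.69 m², the rule gives 116–131% of target (20 ÷ 17.25 and 20 ÷ 15.25), or 29.0–32.8 mg/m². That is above the 90–114% of the other rows. The background section reports 25 mg/m² as the maximum tolerated dose in all age groups and 33 mg/m² as intolerable, the latter when only patients over 12 were eligible. This is a fair reason not to call the row a slip, and it stands. It does not remove the mismatch with the text.

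**The level 0 dose is unambiguous.** Table 1 and the reduction guide agree on 10 mg twice daily. True, but neither agrees with the rule at 0.61–0.69 m².

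**The 20 mg/m² table looks like a leftover.** No dose level in the protocol is defined as 20 mg/m². The table starts at 0.50 m², below the 0.55 m² limit, and reaches single doses of 60 mg (10 + 2 × 25), above the 50 mg maximum. That makes it weak evidence about what Table 1 should say. It is a good reason to explain the table or remove it.

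**The once-daily level -1 dose.** A reader might infer that this contradicts the twice-daily schedule in section 5.1. It does not: 5.1 refers reductions to Appendix D, which gives the step explicitly. From 10 + 10 mg with no smaller capsule, it is the only non-zero reduction.

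**Conclusion.** The dosing instructions conflict in a narrow band. At BSA 0.61–0.69 m², and at 0.60 m² under the table's own handling of ties, Table 1's 10 mg is not what the rule in 5.1 yields; at 0.61–0.69 m² it is 58–66% of target. At 0.66–0.69 m² the 20 mg/m² table in Appendix D also gives a higher daily total than the full dose, with no statement of when it applies. The 50% level -1 step is noted for confirmation, not as a rounding error.

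Three stronger readings are not supported:

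- A reader might infer that the whole row breaks the rule and that the smallest children receive 58–66% of target. At 0.55–0.59 m² the row follows the rule. Children at 0.55–0.60 m² receive 67–73%, a shortfall that comes from the capsule strengths.
- A reader might compare this band with all other bands without limit. The 90–114% range takes the top row only to 2.00 m². With the 50 mg cap, the share falls below 90% above about 2.22 m² (50 ÷ (25 × 2.22) = 90%).
- A reader might infer that response or toxicity would be credited to a dose not given. Section 13 plans no analysis by dose, age or BSA, and the Appendix F diary has fields for dose and times taken.

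The conclusion rests on 10 mg and 25 mg capsules. Section 5.1 also allows another available formulation, whose strengths are not given. No BSA distribution is given either. Entry starts at 3 years and requires swallowing capsules, so the number affected is unknown and may be zero. The Simon design figures do not change.

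**What to change.** The sponsor should reconcile four items: the rounding rule in 5.1, the 0.55–0.69 m² row of Table 1, the same row of the Appendix D reduction guide, and the 20 mg/m² table. If the row is a deliberate exception, 5.1 should say so and give the reason. The purpose of the 20 mg/m² table should be stated, or the table removed. The once-daily level -1 entry should be confirmed as intended. No dose is proposed here, and no view is taken on which passage is right.

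The cost is protocol wording and a table check, with no change to sample size or analysis.

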
Selumetinib plasma pharmacokinetic parameters were similar after single and multiple dosing (days 8, 15 and 22) suggesting minimal accumulation over time after twice daily dosing, consistent with the terminal half-life observed.³⁰

Pharmacodynamics

The effect of selumetinib on ERK phosphorylation in peripheral blood mononuclear cells was evaluated in Part A of study ARRY-0401. Using FACS analysis, the magnitude of pERK relative to baseline was determined in TPA-stimulated pre- and post-treatment blood samples. Selumetinib inhibited TPA-induced ERK phosphorylation at an IC50 of approximately 134 ng/mL (total concentration in plasma). The magnitude of inhibition was found to correlate with plasma selumetinib concentrations. Inhibition of pERK as an indirect measure of MEK inhibition by selumetinib was assessed in PBMCs from each patient at 4 time points post single dose administration across dose levels. Inhibition of ERK phosphorylation was observed at all doses, with greatest inhibition generally occurring at the first time point; 73% inhibition seen at 1 hour.

Phase 1

Accrual to the Pediatric Brain Tumor Consortium's (PBTC) Phase 1 study completed in April, 2013, and the maximum tolerated dose in all age groups was 25 mg/m2/dose, BID. 39 patients

were accrued; one was found to be ineligible. Initially, only patients >12 and \leq 21 years were eligible. Dose levels 1 and 2 (33 and 43 mg/m2/dose, BID) were deemed intolerable with dose limiting toxicities (DLTs) of headache, rash and mucositis. Following de-escalation to dose level 0 (25mg/m2/dose BID), eligibility was extended to patients <12 years. Among the 24 patients treated at dose level 0, no patient <12 years and 3 of 12 patients \geq 12 years experienced DLTs of elevated amylase/lipase, rash, and mucositis. There were 8 sustained responses (1 complete and 7 partial) and the phase 2 study through the PBTC is ongoing.

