3.1.3 Patients must be able to swallow capsules

3.1.4 Age:

Patients must be ≥ 3 years to ≤ 45 years of age at start of treatment

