6 DOSING DELAYS/ DOSE MODIFICATION

6.1 Notification of Study Chair

[figure not shown]
The study chair or co-chair must be notified of any dosage modifications, prior to the implementation of the dose modification

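### A child reduced in the lowest BSA band is re-dosed to 30 mg/day on reaching 0.70 m², 1.5 times the full dose that was not tolerated

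*Combined protocol and SAP*

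**What the plan says.** Section 5.1 sets the dose from a table of BSA bands and applies it afresh each course: "Dosing is based on the BSA calculated at the beginning of each course of therapy for all patients". It then refers the reader to Appendix D for reductions. Appendix D lists a single reduced level by the same bands and states directly below the table: "For all patients, dosing will be based on BSA".

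Section 6.2.1 allows one step down: "Dose de-escalations to dose level -1 are permitted. See Appendix D". A second step ends treatment: "All patients who require dose de-escalation from dose level -1 must be taken off treatment". On oversight, section 6.1 says: "The study chair or co-chair must be notified of any dosage modifications, prior to the implementation of the dose modification".

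No section tells the site to keep a reduced patient on the reduced dose when BSA enters a new band. None caps the new dose at or below the one that caused the toxicity.

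**The concern.** A reduction should leave the patient below the dose that was not tolerated. Here the reduced level is defined by band, and the band is re-read every course. The reduction therefore lasts across a band edge only if level -1 in the upper band is below level 0 in the lower band. At 0.70 m² it is not.

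Two things follow for a child who crosses that edge. The child gets more drug than the amount that led to the reduction, both in mg/day and per m². If toxicity then returns, section 6.2.1 removes the child from treatment for needing to go below level -1, although the dose at that moment was above the original full dose. No endpoint, error rate or analysis is affected; this is a point of individual dosing safety.

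**Working it through.** **Inputs.** Morning plus evening doses from Appendix D; its level 0 column agrees with Table 1 of section 5.1 in all eight bands.

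| Band (m²) | Level 0 (mg/day) | Level -1 (mg/day) | Next band's level -1 ÷ this band's level 0 |
|---|---|---|---|
| 0.55–0.69 | 20 | 10 | 30/20 = **1.50** |
| 0.70–0.89 | 40 | 30 | 35/40 = 0.88 |
| 0.90–1.09 | 50 | 35 | 45/50 = 0.90 |
| 1.10–1.29 | 60 | 45 | 50/60 = 0.83 |
| 1.30–1.49 | 70 | 50 | 60/70 = 0.86 |
| 1.50–1.69 | 80 | 60 | 65/80 = 0.81 |
| 1.70–1.89 | 90 | 65 | 70/90 = 0.78 |
| ≥1.90 | 100 | 70 | – |

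**Cause.** At 25 mg/m² the first band would need 25 × 0.55 = 13.75 mg to 25 × 0.69 = 17.25 mg per dose, but the table gives 10 mg. The full daily dose then doubles at 0.70 m² (20 to 40), and level -1 triples (10 to 30).

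**Per m².** The dose not tolerated lies between 20/0.69 = 29.0 and 20/0.55 = 36.4 mg/m²/day. The reduced dose moves from 10/0.69 = 14.5 to 30/0.70 = 42.9 mg/m²/day across the edge. With B the BSA at reduction, the ratio at 0.70 m² to the child's own not-tolerated dose is (30/0.70)/(20/B) = 1.5 × B/0.70: 1.18 at B = 0.55, 1.29 at 0.60, 1.39 at 0.65 and 1.48 at 0.69.

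**How long it lasts.** The dose stays above the not-tolerated one while 30/BSA > 20/B, that is, while BSA < 1.5 × B. This runs to 0.825 m² for B = 0.55 and through the whole 0.70–0.89 m² band for B ≥ 0.60.

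**Who could be affected.** The documents give no growth rate, so I assume BSA gains of 0.03, 0.05 or 0.07 m² per year. The last recalculation is at the start of course 26, so the time available after a reduction at the start of course r is (26 − r) × 28/365.25 years: 1.687 for r = 4 and 0.997 for r = 13. The lowest BSA at reduction from which 0.70 m² can be reached is 0.70 − rate × time:

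| Reduced at start of | 0.03/year | 0.05/year | 0.07/year |
|---|---|---|---|
| Course 4 | 0.65 | 0.62 | 0.58 |
| Course 13 | 0.67 | 0.65 | 0.63 |

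The highest BSA reached under these rates is 0.69 + 0.07 × 1.840 = 0.82 m² (reduction at the start of course 2). Reaching 0.90 m² would need 0.21/1.840 = 0.114 m² per year.

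**Toxicity frequency.** For the paediatric phase 1 trial, section 2.1.2 reports: "Among the 24 patients treated at dose level 0, no patient <12 years" had a DLT. Since 12 of the 24 were aged 12 or over, this implies 0 of 12, with a one-sided 95% upper bound of 1 − 0.05^(1/12) = 22%. DLTs in that trial are not the same as dose-modifying toxicities here.

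**The case against.** The strongest reply concerns weight. The child must start in the lowest band of a trial open to ages 3 to 45, with at most 9 + 8 = 17 patients per stratum (section 13.2), and section 3.1.3 adds: "Patients must be able to swallow capsules". The toxicity must occur at a dose already below nominal, and it must resolve, because section 5.6.1 ends treatment if it has not done so within 14 days. The child must then grow past 0.70 m² in time. The 1.5 is in raw mg, and 42.9 mg/m²/day is still below the nominal 50. All of this is true, and it lowers the priority.

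A second reply is that safeguards exist: notification of the chair (6.1, 6.2.1), recovery criteria before each course (5.3), and real-time review of dose-modifying toxicities by the chair (12.4). These help but do not settle the point. Notification sets no limit, and a routine change of band may not be seen as a dose modification. A child doing well on 10 mg/day passes 5.3. Section 12.4 is general oversight with no dose rule.

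A third reply is that a plain cap at the earlier level 0 dose would do, and would keep twice-daily dosing. It would remove the inversion: 20 mg/day at 0.70 m² is B/0.70 of the child's own not-tolerated dose per m², which is 21% lower at B = 0.55 but only 1.4% lower at 0.69. It would also return the child automatically to the same 20 mg/day that was not tolerated. That step is better made as an approved decision.

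**Conclusion.** The concern holds. Followed literally, the plan gives a reduced child 30 mg/day at 0.70 m² against 20 mg/day not tolerated: 1.5 times in mg and 1.18 to 1.48 times per m². No other single band edge does this. The table arithmetic is certain. That reduced patients are re-banded is the natural reading of 5.1 and Appendix D, which exempt no one.

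How often it will happen is not known from the documents. It is rare and may be zero, and the estimate of who could be affected rests on assumed growth rates. Whether harm would follow depends on the individual child's sensitivity, which is unmeasured. It should be corrected because a stated rule gives the wrong dose and the correction is almost free; it is not a high-priority point.

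**What to change.** Add to section 6.2.1 and Appendix D, and put an exception referring to 6.2.1 into section 5.1:

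> A patient reduced to level -1 while in the 0.55–0.69 m² band stays on 10 mg/day when BSA moves into the 0.70–0.89 m² band. Any increase needs study chair approval and may not exceed 10 mg twice daily.

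Section 5.1 states: "Selumetinib will be supplied as 10 mg and 25 mg capsules or currently available formulation". With the 10 and 25 mg strengths, the achievable daily doses up to 30 mg are 10, 20, 25 and 30, so 10 is the only one below the 20 not tolerated. Holding it leaves the dose per m² almost unchanged at the edge (14.5 to 10/0.70 = 14.3 mg/m²/day). An approved rise to 20 mg/day gives 20/0.70 = 28.6 mg/m²/day. For a child reduced at 0.69 m² (29.0 not tolerated) that is in effect a rechallenge.

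The cost is one sentence in two places and a cross-reference. The clinical downside is that a held child receives a third of what others at level -1 in the new band receive: 14.3 against 42.9 mg/m²/day at 0.70 m², 12.2 against 36.6 at 0.82 m², and 11.2 against 33.7 at 0.89 m². Chair approval provides the way up. The rule binds on this band move only.

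A separate editorial point, on which nothing above depends: the 20 mg/m² twice-daily table in Appendix D is not tied to either dose level and should be labelled or deleted.
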